4. Optional Procedure: With the patient's consent, if the patient cannot receive the co-stimulated T cells, the cells will remain cryopreserved in the Stem Cell Laboratory indefinitely. The patient can receive the cells at a later date. If the patient's physician feels that the patient will no longer benefit from the cells,

the cells may be used for research or discarded. If the patient refuses, the cells will be destroyed.

Study Enrollment:

The study population for this research will consist of participants from:

Only at MDACC

Estimated Accrual:

Total Accrual at MDACC:	40
Estimated monthly accrual at MDACC:	1

Accrual Comments:

The sample size of 40 patients was chosen for logistical reasons.

Is this an NCI-Cancer Therapy Evaluation Protocol (CTEP)? No

Is this an NCI-Division of Cancer Prevention Protocol (DCP)? No

Statistical Considerations:

Overview

This is a phase II trial of infusion of autologous T cells for immune restoration in patients with CLL. The primary scientific goal is to determine the feasibility and safety of this procedure. A total of 40 patients will receive T cell infusions. Endpoint evaluation will be at day +90 after the co-stimulated T cell infusion.

Sample Size

In this trial, the sample size of 40 patients was chosen for logistical reasons. With 40 patients, a 95% confidence interval around the success rate will be no wider than 32%.

Primary Endpoint

Success will be defined as achievement of a target activated T-cell dose of $1 \times 10^8 \pm 20\%$ and the lack of dose limiting toxicity (DLT).

For this trial DLT is defined as:

- Any grade 4 or higher non-hematologic toxicity or grade 3 or 4 allergy/immunology toxicity;
- Allergic reaction or urticaria grade 3 or higher (CTC v4.03 CTCAE) by +90 days after T cell infusion;
- Grade 2 or greater autoimmune phenomena; or,
- Grade 4 or higher hematologic toxicity (with the exception of any preexisting AE due to prior treatment or due to disease) deemed related to T cells and occurring by day +90 after T cell infusion.

Feasibility is defined as achievement of the target T cell dose ($1 \times 10^8 \pm 20\%$) without DLT in > 50% of patients enrolled.

Safety Monitoring

Any death due to the infusion of co-stimulated T-Cell product itself and not disease progression will be considered unacceptable and the study will be stopped. If the study is not terminated early, it will continue

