until all patients have been treated with co-stimulated T Cells and completed all follow up evaluations.

In addition, we will use a Bayesian sequential monitoring rule to monitor the primary endpoint of the study. If there is a high probability that the overall success rate is less than 50%, enrollment into the trial will be stopped. We will enroll a minimum of 6 patients onto the study before stopping. We will use the following criteria: we will stop enrollment if at any time during the course of the trial:

$\Pr [\text{90-day success rate} > 0.50 \mid \text{data}] < 0.025$

That is, if we determine that there is a less than 2.5% chance that the 90-day success rate is greater than 50%, accrual will be stopped. We assume a beta (1, 1) prior distribution for the success rate, which has a mean of 0.50 corresponding to the target success rate. Stopping boundaries corresponding to this probability criterion are to terminate accrual if:

If there are this many patients accrued	Stop the trial if this number of patients meet criteria for success
6-7	0
8-10	0-1
11-13	0-2
14-15	0-3
16-18	0-4
19-21	0-5
22-23	0-6
24-26	0-7
27-28	0-8
29-31	0-9
32-33	0-10
34-35	0-11
36-38	0-12
39	0-13
40	Always Stop

This stopping rule was chosen to assure that the probability that the trial will stop early would be approximately 10% if the true success rate was 50%. The operating characteristics of this rule are shown in the table below.

We will enroll 3 patients and then wait till all 3 have reached +90 days without DLT before enrolling more patients. At that time point 3 additional patients will be enrolled and we will wait till they have all reached

+90 days and without DLT before enrolling the remaining patients.

Operating Characteristics for Success Monitoring Rule

If the true 90-day success rate is...	Early Stopping Probability	Achieved Sample Size		
		25th percentile	50th percentile	75th percentile
0.3	0.833	8	16	32
0.4	0.413	19	40	40
0.5	0.108	40	40	40
0.6	0.018	40	40	40
0.7	0.002	40	40	40

The monitoring rules will be assessed by the study team with assistance as necessary from the Department of Biostatistics at MD Anderson Cancer Center.

Secondary Analyses

Immune reconstitution: We will assess the percentages and absolute values of CD3+, CD4+, CD8+ and CD4/CD8 ratio and report these at each time point along with 95% confidence intervals. In addition, immune reconstitution will be compared at each time point.

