Overall Response (CR+PR): We will assess overall response (CR+PR).

Infections: We will assess the rates of infection.

Criteria for Removal from Study:

1. **"Subjects" voluntary withdrawal from protocol.**
2. **Noncompliance of the patient with protocol requirements**
3. **After 5 years of treatment completion**
4. **Subject lost to follow-up**
5. **Decision by the investigators that withdrawing is in the subject's best interest**
6. **Pregnancy**
7. **Termination of the study by the investigator, IRB, or FDA**
8. **Unacceptable toxicity and other safety reasons- as defined by the stopping rules below.**
9. **Patients who experience DLT will not be eligible for retreatment.**

Toxicity Management, Stopping Rules and Study Termination

Only unexpected SAEs that are related to the activated autologous T cells would define a stopping rule.

Management of toxicity

Autoimmune toxicity associated with activated autologous T cells has been managed with a course of pharmacologic immunosuppression such as systemic corticosteroids.

Dose Limiting Toxicity

Dose limiting toxicity (DLT) is defined as any one or more of the following which occur after the T Cell Infusion:

1. Any Grade 3 or higher non-hematological adverse event other than fevers lasting less than 72 hours must will be considered DLT. Any prolonged grade 4 or higher hematologic toxicity (longer than 7 days) due to study treatment will be considered as DLT (CTC v4.03 CTCAE).
2. Allergic reaction or urticaria grade 3 or higher and deemed related to T cells (as determined using the Common Terminology Criteria for Adverse Events v4.03).
3. Grade 2 or greater autoimmune phenomena
4. Grade 4 or higher hematologic toxicity with the exception of any preexisting AE due to prior treatment or due to disease.

Stopping Rules

The statistical considerations section describes the primary stopping rule for the study, a rule which monitors patient success rate.

In addition, accrual to the study will be suspended to allow review with the institutional IRB if any death occurs among subjects who receive investigational agents due to the infusion of co-stimulated T-Cell product itself and not disease progression.

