If the study is prematurely halted based on preliminary information, it will be allowed to continue only if it is determined upon review that the incidence of adverse events is not exceedingly high for this patient population and that any death is not primarily due to the co-stimulated T-Cell therapy. If the study is not terminated early, it will continue until all patients have been treated with co-stimulated T Cells and completed all follow up evaluations.

Data Safety Monitoring Board / DSMB at MDACC:

Select the name of the data safety monitoring board (DSMB) monitoring this protocol:
Not Applicable

Please explain:

As of PDOL Version 07, this study is not randomized nor blinded.

Protocol Monitoring:

Does this protocol have a schedule for interim and final analysis? Yes

Provide a summary or schedule of interim analysis.

We will use a Bayesian sequential monitoring rule (Thall et al (ref)) to monitor the primary endpoint of the study. See the Statistical Considerations section for details.

Protocol Monitoring Plan:

Patient registration and monitoring will be performed by the MD Anderson IND Office according to institutional policies.

Intellectual Property:

1. Does this study include any agents, devices, or radioactive compound (or No drug) manufactured at MD Anderson Cancer Center or by a contract manufacturer?

Investigational New Drugs (IND):

Does this protocol require an IND? Yes

Who is the IND Holder/Regulatory Sponsor?

MD Anderson

IND Number: 16501

Please "Compose" an Investigator's Brochure Cover Letter. For technical assistance, contact the PDOL Help Desk, [contact].

Investigational Device (IDE):

Does this study utilize an Investigational Device? No

Moon Shots Program

Will your protocol be funded by the Moon Shots Program? Yes

Specific Disease Site(s): Chronic Lymphocytic Leukemia (CLL)

Platform(s): Applied Cellular Therapy (ACT)

Sponsorship and Support Information:

Does the Study have a Sponsor, Supporter or Granting Agency? Yes

Sponsor Name: Moon Shot Program

Support Type: Other: CLL

This Sponsor/Supporter/Granting Agency will receive data.

Regulatory Requirements

Radioactive Material:

Does this study involve the administration of radioisotopes or a radioisotope labeled agent?

No

[Click here for help](#)

Biosafety:

Does this study involve the use of Recombinant DNA Technology? No

Does this study involve the use of organisms that are infectious to humans? No

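### A death caused by the T-cell product stops the study under one section but only suspends accrual under another, and the restart clause uses a different attribution test

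*Combined protocol and SAP*

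**What the plan says.** Three provisions deal with a death caused by the product.

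- **Statistical Considerations, Safety Monitoring.** The trigger is "Any death due to the infusion of co-stimulated T-Cell product itself and not disease progression". The consequence is that a death from the product and "not disease progression will be considered unacceptable and the study will be stopped". No review or restart step is given there.
- **Toxicity Management, Stopping Rules and Study Termination, under Stopping Rules.** The trigger is a death among subjects who "receive investigational agents due to the infusion of co-stimulated T-Cell product itself and not disease progression". The consequence is that "accrual to the study will be suspended to allow review with the institutional IRB". Infusions are not mentioned.
- **Closing paragraph of Stopping Rules.** This begins "If the study is prematurely halted based on preliminary information" and allows continuation only if review finds that adverse events are not excessive for the population (no threshold is given) and that "any death is not primarily due to the co-stimulated T-Cell therapy".

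Safety Monitoring and the closing paragraph of Stopping Rules both add that a study not terminated early runs until every patient has been treated and followed up.

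On enrolled patients, the Proposed Treatment/Study Plan has a 14-day expansion before infusion and allows retreatment 6-12 months after the first infusion. The only stated bar on retreatment is the patient's own DLT.

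**The concern.** The first two provisions share a trigger, almost word for word, but order different actions. A study team facing such a death would find one section telling it to stop the study and another telling it to pause accrual and consult the IRB. The section with the accrual suspension refers to the statistical section only for the success-rate rule. It then adds its own death rule without saying how that rule relates to the stop.

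Two things are at stake. The first is whether patients already enrolled keep receiving the product while a death attributed to it is under review. The second is which attribution standard decides between closure and resumption. Safety is part of the primary objective, no DSMB is assigned, and the study team assesses the monitoring rules, so the written rule carries most of the weight.

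**Working it through.** **The plan's own figures.** The death rule has no stated figure. The nearest is the success-rate rule: beta(1,1) prior, stop if the posterior probability of a success rate above 0.50 is below 0.025, minimum 6 patients. Exact binomial recursion over patients 6 to 39 matches every printed boundary and gives early stopping probabilities of 0.833, 0.413, 0.108, 0.018 and 0.002 at true rates of 0.3, 0.4, 0.5, 0.6 and 0.7. These equal the protocol's table. None of them depends on the death rule.

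**The three provisions side by side.**

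| Place | Trigger or test | Action | Infusions mentioned? |
|---|---|---|---|
| Safety Monitoring | Death due to the product itself, not progression | Study stopped | No, though a stop can be read to include them |
| Stopping Rules | Same | Accrual suspended for IRB review | No |
| Stopping Rules, closing paragraph | Death not *primarily* due to the therapy, and adverse events not excessive | Halted study may continue | No |

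**What suspending accrual covers.** The success-rate rule in Safety Monitoring uses two words for one action: "we will stop enrollment if at any time during the course of the trial" and, in restating the same criterion, "chance that the 90-day success rate is greater than 50%, accrual will be stopped". Accrual therefore means enrollment in this protocol. Suspending it does not by its terms reach a patient already enrolled.

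**A mixed-cause death.** Suppose both product and disease contributed. Whether the trigger is met is unclear, because it requires the product itself and excludes progression. If it is met, Safety Monitoring stops the study, while the closing paragraph would allow resumption if the product was not the primary cause. The two standards can give different answers for the same death.

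**Patients awaiting a first infusion.** Inputs: 1 patient per month (Estimated Accrual) and a 14-day expansion (Proposed Treatment/Study Plan). Assumptions: blood is collected at enrollment, cells are infused on day 14, and accrual is steady.

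- Mean waiting = 1 × 14/30.44 = 0.46 patient.
- With Poisson arrivals (assumed), P(at least 1) = 1 − exp(−0.46) = 0.37.
- P(at least 2) = 1 − exp(−0.46) × (1 + 0.46) = 0.08.

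Steady accrual does not describe the two opening groups of 3. No stagger within a group is stated, so up to 2 others in a group could still be waiting.

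**Patients in the retreatment window.** The window lasts 12 − 6 = 6 months.

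- Mean in the window = 1 per month × 6 months = 6 patients, once accrual has been steady for long enough.
- This is an average. With Poisson arrivals, P(more than 6) is about 0.39.
- Patients with a prior DLT, no stored cells or no need must be taken off. The documents do not give those shares, so the number who could actually be retreated may be zero.

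**The case against.** The strongest reply is that the provisions form a workable sequence: suspend on preliminary information, review, then resume or close, with a confirmed product death closing the study. This largely stands for the two Stopping Rules provisions. It does not absorb the Safety Monitoring sentence, which stops the study with no review step, and the protocol nowhere states the sequence.

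A reader might infer that nothing in the protocol would end infusions after such a death. That goes too far. Safety Monitoring stops the study, and the adjoining sentence makes treating all patients a consequence of not terminating early, so a stop naturally ends treatment too. The Criteria for Removal from Study also allow withdrawal in the subject's interest (item 5), on study termination (item 7), and for safety reasons tied to the stopping rules (item 8). The gap arises when the accrual suspension is applied alone. In practice the investigators or the IRB would probably pause dosing, and institutional policies that the documents only mention might require it.

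A reader might also infer that mixed-cause deaths are not addressed at all. The restart clause does address them once a halt has occurred, through the word *primarily*. Only the initial trigger is unclear.

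Nor does the sentence limiting stopping rules to unexpected, related SAEs contradict the death rule. A death caused by the product is a related SAE, and nothing in the documents lists death as expected. That sentence conflicts only with the success-rate rule, which is a matter of wording.

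**Conclusion.** The inconsistency is real and should be fixed. One trigger leads to an outright stop in one section and an accrual suspension in another, and the test for continuing uses a different attribution standard. A team could not follow all three provisions as written after a product-related death.

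The exposure is modest. It applies only if the suspension is followed without the stop: about 0.5 patient on average awaiting a first infusion, and about 6 on average in the retreatment window, of whom an unknown number, possibly none, could be retreated. These figures rest on the stated accrual rate, steady accrual, collection at enrollment and infusion at day 14. Six is a mean and should not be taken as a ceiling.

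No boundary or operating characteristic is affected. The header lists this version as terminated, so the point concerns the plan as written and any reuse of it.

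**What to change.** State one rule and repeat it identically in Safety Monitoring, Stopping Rules and the restart paragraph:

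- A death attributed on preliminary information to the T-cell product immediately suspends accrual and all T-cell infusions, including retreatment, pending IRB review.
- The study closes if review confirms attribution; otherwise it may resume.
- Attribution is judged by one threshold phrase used in all three places, which also says how a death with both product and disease causes is classed.

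The cost is a wording amendment, plus a temporary pause if the death is later judged unrelated. Under the Optional Procedure, cells can stay cryopreserved for later use with the patient's consent. A patient who refuses storage would lose the expanded cells. On the figures above, that is at most about 0.5 patient on average.
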